2.6.2. Demographics and Medical History

Baseline demographic information will be collected during screening, and will include age, sex and race/ethnicity.

Relevant medical history includes all ongoing medical or surgical issues. Remote medical and surgical history > 5 years from the time of screening should only be included if considered relevant to the study.

2.6.3. Vital Signs

Vital Signs include heart rate and blood pressure

2.6.4. Electrocardiograms

12-Lead ECGs will be collected at Day 1 and at the Day 180 visit only, unless clinically indicated.

2.6.5. Physical Examination

The physical examination should include a focused examination, which may include general, respiratory, cardiovascular, abdominal, extremities, and recording of height, weight.

The physical examination should also include a full neurologic evaluation as described in Appendix A of protocol.

2.6.6. Clinical Laboratory Assessments

Specimens will be obtained at the time points in the Schedule of Assessments ([Table 1](#)). Additional aliquots of plasma or serum will be collected at each time point and stored for any clinically indicated efficacy or safety analyses to be conducted at the end of the study.

Subjects will be in a fasted state for all clinical laboratory assessments. Screening lab tests will be performed by the Central Lab, with the exception of urinalysis and pregnancy test, which will be done in-house at the participating institution's laboratory using testing materials supplied by the Central Lab. Results from these screening tests must be available before the start of study drug injection on Day 1 to confirm subjects meet eligibility criteria.

Laboratory assessments will include:

Biochemistry: AST, ALT, alkaline phosphatase (ALP), gamma glutamyl transferase (GGT), uric acid, total bilirubin (TBIL), direct bilirubin, indirect bilirubin, lactate, bicarbonate, sodium, creatine kinase (CK), albumin, total protein urea (BUN), creatinine, potassium, chloride, glucose (fasting), inorganic phosphate, eGFR, calcium, and tryptase (as required).

Inflammatory markers: hsCRP (fasting), IL6, IFN- γ , and TNF- α

Hematology: hemoglobin, hematocrit, erythrocytes, reticulocytes, platelet counts, mean cell hemoglobin (MCH), mean corpuscular volume (MCV), mean corpuscular hemoglobin concentration (MCHC), white blood cell count, differential blood count.

Coagulation: prothrombin time (PT), international normalized ratio (INR), activated partial thromboplastin (aPTT).

HbA1c: hemoglobin A1c

Urinalysis: Urinalysis will be performed at the time points defined in the Schedule of Assessments and evaluated by dipstick analyses at the investigational site local lab (a standardized dipstick test will be supplied by the Central Lab). Urinalysis will be performed from a sample of mid-stream urine. In case of abnormal results, microscopy and other assessments will be performed at the local lab. The following parameters will be assessed: Nitrite, protein, glucose, ketone, urobilinogen, bilirubin, red blood cells (RBC)/erythrocytes, white blood count (WBC)/leukocytes, pH, urine sediment (microscopic examination will be performed in the event of abnormalities).

Urine pregnancy: Urine pregnancy testing will be conducted locally at the visits specified in the Schedule of Assessments (a standardized pregnancy test will be supplied by the Central lab).

2.6.7. Anti-Inclisiran Antibodies

Additional sample for analysis of the induction of antibodies will be collected at the time points in the Schedule of Assessments ([Table 1](#)).

Aliquots of serum samples will be obtained and frozen, to permit future analysis of the effect of inclisiran on the expression of these exploratory biomarkers. Biological samples for biomarker research will be retained on behalf of the Sponsor for one year following the last subject's last visit in the study.

2.7. Assessment of Efficacy

Specimens for assays of lipids/lipoproteins will be obtained at the time points in the Schedule of Assessments ([Table 1](#)). Subjects will be in a fasted state for all efficacy laboratory assessments. Parameters to be assessed will include: total cholesterol (TC), triglycerides, LDL-C, HDL-C, non-HDL-C, very low-density lipoprotein (VLDL-C), apolipoprotein A1 (Apo-A1), apolipoprotein B (Apo-B), lipoprotein(a) [Lp(a)], and PCSK9.

2.7.1. Change in LDL-C

The primary efficacy endpoint is the percentage change in LDL-C at Day 90 and Day 180.

In addition, this study will assess change and percentage change in LDL-C from Day 1 to each subsequent visit until Day 180 or final visit as a secondary efficacy endpoint .

Blood samples for determination of LDL-C (β -quantification) concentrations will be collected at the time points in the Schedule of Assessments.

2.7.2. Change in Lipids/Lipoproteins

Secondary efficacy assessments will include measurement of the effects of inclisiran on levels of lipids and lipoproteins including total cholesterol, triglycerides, LDL-C, HDL-C, non-HDL-C, VLDLC, Apo-A1, Apo-B, Lp(a), and PCSK9.

- Change and percentage change in PCSK9 levels
- Change and percentage change in other lipids, and apolipoproteins
- **Biomarkers** (stored samples): Additional aliquots of plasma and serum will be collected at each time point and stored for additional analyses, including future analysis of biomarkers of CV risk. These samples will be retained for 1 year following the last subject's last visit in the study.

Plasma samples will be analyzed using a validated enzyme linked immunosorbent assay to determine PCSK9 protein concentration. Full details of the analytical methods used will be described in a separate bioanalytical report.

2.8. Assessment of Pharmacogenetics

A blood sample will be collected, preferably during screening, only from subjects who sign a separate consent for pharmacogenetics. Samples will be processed as described in the Laboratory Manual and stored. Genetic assessment will be performed by an accredited laboratory. This assessment will determine if there is a different response for LDL-C lowering based on the type of mutation(s).

3. ADVERSE EVENTS

3.1. Adverse Event

Adverse Event (AE): Any untoward medical occurrence in a patient or clinical trial subject administered a medicinal product and which does not necessarily have a causal relationship with this treatment. An adverse event can therefore be any unfavorable and unintended sign (eg, an abnormal laboratory finding), symptom, or disease temporally associated with the use of a medicinal product, whether or not considered related to the medicinal product.

Planned hospital admissions and/or surgical operations for an illness or disease that existed before the study drug was given or the subject was randomized in a clinical study are not to be considered AEs.

Adverse events or abnormal test findings will be followed until the event (or its sequelae) or the abnormal test finding resolves or stabilizes at a level acceptable to the Sponsor/Investigator.

3.2. AE Severity

The severity of an AE will be assessed by the investigator. The investigator should ensure that any subject experiencing an AE receives appropriate medical support until the event resolves.

Adverse events will be graded on a 3-point scale and reported as indicated on the case report form. The intensity of an AE is defined as follows:

- 1 = Mild: Discomfort noticed, but no disruption to daily activity.
- 2 = Moderate: Discomfort sufficient to reduce or affect normal daily activity.
- 3 = Severe: Inability to work or perform normal daily activity.

3.3. Study Drug Causality

The relationship of an AE to study treatment will be assessed with consideration to the following criteria:

- Temporal relationship to the initiation of study medication
- Response of the event to withdrawal of study medication
- AE profile of concomitant therapies
- Clinical circumstances during which the AE occurred
- Subject's clinical condition and medical history

Categorization of causality will be designated by the investigator as stated below:

Reasonable possibility - There are facts (evidence) or arguments to suggest a causal relationship between the event and the IMP.

No reasonable possibility – There are few to no facts (evidence) or arguments to suggest a causal relationship between the event and the IMP

3.4. Serious Adverse Event

A serious adverse event (SAE) is any untoward medical occurrence that at any dose:

- Results in death,
- Is life-threatening, i.e., the subject was, in the opinion of the investigator, at immediate risk of death from the event as it occurred (it does not include an event that, had it occurred in a more severe form, might have caused death),
- Results in a significant, persistent or permanent change, impairment, damage or disruption in the subject's body function/structure, physical activities and/or quality of life,
- Requires in-subject hospitalization or prolongs hospitalization,
- Is a congenital anomaly/birth defect, or
- Is another medically significant event where medical and scientific judgement should be exercised in deciding whether other situations should be considered serious reactions, such as important medical events that might not be immediately life threatening or result in death or hospitalization but might jeopardize the subject or might require intervention to prevent one of the other outcomes listed above. Examples of such events are intensive treatment in an emergency room or at home for allergic bronchospasm, blood dyscrasias or convulsions that do not result in hospitalization or development of dependency or abuse. Any suspected transmission via a medicinal product of an infectious agent is also considered a serious adverse reaction.

A distinction should be drawn between serious and severe AEs. Severity is an estimate or measure of the intensity of an AE, while the criteria for serious AEs are indications of adverse subject outcomes for regulatory reporting purposes. A severe AE need not necessarily be considered serious and a serious AE need not be considered severe. For example, nausea that persists for several hours may be considered severe nausea, but not an SAE. On the other hand, an MI that may be considered minor could also be an SAE if it prolonged hospitalization.

3.5. Medication Errors

Medication error refers to any unintended error in the dosing and administration of the study product as per instructions in the protocol. Medication Errors generally fall into four categories as follows:

1. Wrong study drug
2. Wrong dose (including dosing regimen, strength, form, concentration, amount, including above the maximum or under the minimum recommended dose);
3. Wrong route of administration;
4. Wrong patient (i.e., not administered to the intended subject)

3.6. Adverse Events of Special Interest (AESIS)

An adverse event of special interest (serious or nonserious) is one of scientific and medical concern specific to the Sponsor's study drug or program, which warrants ongoing monitoring and rapid communication by the investigator to the sponsor. Such an event might warrant further investigation in order to characterize and understand it.

The following AESI(s) have been identified for the study drug inclisiran in this protocol. •
Injection site reactions (ISR)

Injection site reactions including individual signs or symptoms at the injection site reported following study drug administration will be collected as an AESI.

The grade (severity) of injection site reaction will be determined by the Common Terminology Criteria for Adverse Events (CTCAE) criteria of Injection Site Reaction (General disorders and administration site conditions) (see [Table 2](#)).

Table 2: Common Terminology Criteria for Adverse Events (CTCAE) criteria of Injection Site Reaction

Grade I:	Tenderness with or without associated symptoms (eg, warmth, erythema, itching)
Grade II:	Pain; lipodystrophy; edema; phlebitis
Grade III	Ulceration or necrosis; severe tissue damage; operative intervention indicated
Grade IV	Life-threatening consequences; urgent intervention indicated
Grade V	Death

Abbreviations: AE = adverse even

Reference source: Common Terminology Criteria for Adverse Events (CTCAE), Version 4.0, Published May 28, 2009

4. MEASURES TO MINIMIZE/AVOID BIAS

This is an unblinded, open label study. The primary endpoint is based on an assessment of LDL-C, which is a measurement that is not likely to be subject to interpretation bias

5. STATISTICAL PLAN

This is an 8-10 subject non-randomized pilot study. Subjects with homozygous familial hypercholesterolemia will be recruited from approximately 5 sites globally. Subjects that qualify for entry into the study will be enrolled to receive inclisiran. The primary objective of this study is to characterize the effect of 90 and 180 days of subcutaneous inclisiran on the percent change from Day 1 in low-density lipoprotein cholesterol (LDL-C) in subjects with homozygous familial hypercholesterolemia.

The primary hypothesis is that inclisiran, when used in combination with maximally tolerated statin therapy with or without ezetimibe, will be well-tolerated, will suppress circulating PCSK9 >70% and will result in reduction of LDL-C, defined as mean percent change from Day 1 following 90 and 180 days of treatment, in subjects with homozygous familial hypercholesterolemia.

5.1. Sample Size

The sample size was chosen based on clinical considerations.

5.2. General Statistical Considerations and Definitions

5.2.1. General Statistical Methods

All study-collected data will be summarized by treatment group using descriptive statistics, graphs, and/or raw data listings. Categorical variables will be summarized using counts and percentages. Percentages are based on the number of subjects in the analysis set for whom there are non-missing data, unless otherwise specified. Continuous variables, including changes from day 1, will be summarized using descriptive statistics (n, mean, standard deviation [SD], median and interquartile range [first and third quartiles], minimum and maximum). All summaries are presented for all subjects due to the small sample size in this study.

The Statistical Analysis Plan (SAP) will be finalized before database lock.

Statistical analyses will be carried out using SAS statistical analysis software version 9.2 or higher (SAS Institute, Inc., Cary, North Carolina, USA).

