4.4. Withdrawal Criteria

All subjects have the right to withdraw at any point during treatment without prejudice. The investigator can discontinue any subject at any time if medically necessary. It will be documented whether or not each subject completed the clinical study. If for any subject study treatment or observations were discontinued, the reason will be recorded and the Sponsor should be notified promptly. Reasons that a subject may discontinue participation in a clinical study are considered to constitute one of the following:

- Adverse event(s)
- Death
- Subject withdrew consent
- Physician decision
- Lost to follow-up

Upon occurrence of a serious or intolerable AE, the investigator or designee will make every possible attempt to confer with the Sponsor and the SC before discontinuing the subject.

It is imperative to obtain complete follow-up data for all subjects whether or not they receive their study treatment or have discontinued ALN-PCS_{SC}. All data collected up until the time of subject withdrawal is to be entered into the electronic case report form (eCRF). In addition, every attempt should be made to collect follow-up information except for those subjects who specifically withdraw consent to release of such information. All procedures and laboratory specimens or tests requested for evaluation following administration of ALN-PCS_{SC} should be carried out when possible whether or not a subject continues to receive treatment according the protocol. Subjects will not be replaced in this trial.

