10.3.4. Missing Data Handling

Missing data will not be imputed.

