5.2.2.1. Modified Intent-to-Treat (mITT) Population

All ITT subjects (who receive at least one dose of study drug), who have baseline and at least one post-baseline measurement for the primary endpoint. This will be the primary population for the efficacy analyses; unless specified otherwise, the mITT will be the default analysis set in this study.

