5.2.2.2. Safety Population

All subjects who received at least one dose of study drug. Treatment classification will be based on the actual treatment received. This will be the primary population for the safety analyses.

The primary analysis set is the modified Intent-to-Treat (mITT), which will include all enrolled subjects who have received at least one dose of study drug. Unless specified otherwise, the mITT will be the default analysis set in this study.

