5.2.4. Missing data handling

Unless otherwise specified, missing data will not be imputed and will be excluded from the associated analysis.

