5.3.6. Efficacy Analysis

5.3.6.1. Primary Efficacy Endpoints

The primary endpoint is the percent change in LDL-C following 90 and 180 days of treatment.

Summary statistics and 95% CI of this primary endpoint will be provided. Changes of LDL-C from Day 1 by scheduled visits will also be summarized. Response rate of subjects with 15% or greater reduction in LDL-C from Day 1 following 90 and 180 days of treatment will be calculated.

The analysis for the primary endpoint will be descriptive. Means and confidence intervals will be provided. Mean plots with standard error bars will be provided for observed LDL-C value, change in LDL-C value, and percent change in LDL-C value.

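### The 15% LDL-C response rate is an observed-case rate whose denominator can shrink visit by visit; with 8-10 subjects, an all-dosed rate should be printed beside it

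*SAP*

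**What the plan says.** The responder analysis is in SAP 5.3.6.1: "Response rate of subjects with 15% or greater reduction in LDL-C from Day 1 following 90 and 180 days of treatment will be calculated". That section names no denominator and does not say how a missing value is classified.

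Two general rules fill the gap. SAP 5.2.1 says: "Percentages are based on the number of subjects in the analysis set for whom there are non-missing data". A closing clause of that sentence allows an exception, but none is made for this rate. SAP 5.2.4 says that, by default, "missing data will not be imputed and will be excluded from the associated analysis". Protocol 10.3.4 is shorter: "Missing data will not be imputed". It gives no denominator rule.

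The analysis set is defined in two ways. SAP 5.2.2.1 takes dosed subjects "who have baseline and at least one post-baseline measurement for the primary endpoint". SAP 5.2.2.2 describes the same mITT set as one "which will include all enrolled subjects who have received at least one dose of study drug".

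The trial is to enrol 8-10 subjects. Protocol 4.4 adds: "Subjects will not be replaced in this trial". The same section, and Protocol 4.4.1, ask that follow-up data be obtained even when study drug is stopped.

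**The concern.** The rate will be read as a proportion of the treated subjects, and the SAP 5.2.2.2 wording of the mITT set encourages that reading. What the rules produce is a proportion of those with an LDL-C value at the visit. If one or two subjects have no value, the denominator falls by one or two out of 8-10, and nobody is recruited in their place. The Day 90 and Day 180 rates can then rest on different subjects, so a change between them could partly reflect who was measured.

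The reasons for leaving the study listed in Protocol 4.4 include adverse events, death, physician decision and loss to follow-up. With such reasons, it cannot simply be assumed that missingness is unrelated to response.

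**Working it through.** **Inputs.** N = 8 to 10 (SAP 1.1, SAP 5). No replacement (Protocol 4.4). Non-missing denominator (SAP 5.2.1). Missing values excluded (SAP 5.2.4). The documents give no dropout rate, expected response rate or power figure, so there is no figure of the plan's own to reproduce. I assume 1 or 2 missing LDL-C values at a visit, and that every dosed subject has a Day 1 value.

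**Which rule applies.** SAP 5.3.6.1 specifies nothing different, so the default holds. The choice between the two mITT definitions does not matter here. A subject with no post-baseline LDL-C at all is outside the set under SAP 5.2.2.1; under SAP 5.2.2.2 that subject is in the set but removed by the non-missing condition. A subject missing only one of the two visits is removed from that visit under either definition.

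**Formulas.** Let n be the number dosed, d the number missing at the visit, k the observed responders, and r the unobserved number of responders among the d missing.

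- Rate under the SAP: k/(n−d)
- All-dosed rate, missing as non-response: k/n
- All-dosed rate, missing as response (upper bound): (k+d)/n
- True all-dosed rate: (k+r)/n

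**Gap between the first two rates.** k/(n−d) − k/n = kd/[n(n−d)]. This is zero when k = 0 and largest when every observed subject responds (k = n−d), where it equals d/n.

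| n | d | Range of gap over all k (percentage points) |
|---|---|---|
| 8 | 1 | 0 to 1/8 = 12.5 |
| 8 | 2 | 0 to 2/8 = 25.0 |
| 10 | 1 | 0 to 1/10 = 10.0 |
| 10 | 2 | 0 to 2/10 = 20.0 |

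**Examples.**

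| n | d | k | SAP rate | Missing as non-response | Missing as response |
|---|---|---|---|---|---|
| 8 | 1 | 5 | 5/7 = 71.4% | 5/8 = 62.5% | 6/8 = 75.0% |
| 8 | 2 | 5 | 5/6 = 83.3% | 5/8 = 62.5% | 7/8 = 87.5% |
| 10 | 2 | 6 | 6/8 = 75.0% | 6/10 = 60.0% | 8/10 = 80.0% |

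**Direction against the truth.** k/(n−d) exceeds (k+r)/n exactly when k/(n−d) > r/d, that is, when the missing subjects respond less often than the observed ones. In the first example, if the missing subject would not have responded, 71.4% is too high against 62.5%. If that subject would have responded, 71.4% is too low against 75.0%.

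**The case against.** A reader might infer that the rate is inflated whenever data are missing. The documents do not support that. Any observed-case rate with at least one responder lies above a rate that counts missing as non-response; that follows from the choice of comparator. Bias against the true all-dosed rate depends on responses nobody has seen, and the first example can go either way.

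A reader might also infer that every dropout disappears from the rate. That is too broad. Removal is per visit and only when LDL-C is missing. Protocol 4.4 and 4.4.1 ask for continued follow-up, so a subject who stops drug but is still measured stays in both rates, and one lost after Day 90 stays in the Day 90 rate.

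Three further points are fair:

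- The non-missing rule is stated openly and is a common convention, so the SAP does not mislabel the rate.
- Counts accompany percentages (SAP 5.2.1) and all data are listed (SAP 5.2.3), so with 8-10 subjects a careful reader could recompute the rate.
- Sampling uncertainty is large in any case. The exact 95% interval is 35.9-99.6% for 5/6 and 24.5-91.5% for 5/8.

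Counting missing as non-response is itself a form of single imputation. It would depart from Protocol 10.3.4, while SAP section 7 declares no changes to the protocol's analyses. This argues against replacing the observed-case rate. It does not argue against a second, labelled row.

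What remains is that the plan sets no all-dosed figure and does not commit to showing the number missing per visit beside this rate.

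**Conclusion.** The point holds as a limited one. Under SAP 5.2.1 and 5.2.4 the 15% response rate is an observed-case rate with a denominator that may differ between Day 90 and Day 180. It is at or above the all-dosed, missing-as-non-response rate, by at most 10-12.5 points for one missing value and 20-25 points for two across N=10 to N=8. Those sizes rest on an assumed one or two missing values; with none missing there is no gap. Overstatement of the true all-dosed rate needs the further condition that missing subjects respond less often than observed ones.

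It would be a mistake to read this as undermining the Phase III decision. SAP 1.1 and Protocol 3.1 tie that decision to an observed mean LDL-C reduction of 15% or more and say that the small sample will be weighed. SAP 5.3.6.1 calls the analysis descriptive, and the response rate is not listed among the secondary or exploratory endpoints. No test or pass mark rests on it. The change is a cheap improvement.

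**What to change.** In SAP 5.3.6.1, keep the observed-case rate and add wording such as: *At each of Day 90 and Day 180, the 15% response rate will also be given over all dosed subjects with a Day 1 LDL-C, counting a missing value at that visit as non-response. Both rates will be shown as n/N, with the number missing.*

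Record the added row in SAP section 7 as an addition to the protocol's analyses, because Protocol 10.3.4 rules out imputation. Naming the denominator explicitly also makes the added rate independent of which mITT definition is used, although SAP 5.2.2.1 and 5.2.2.2 should still be reconciled. SAP 5.2.1 foresees finalisation ahead of database lock; the rule is best fixed by then, before the pattern of missing values can influence it.

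Cost: one table row per visit, one SAP sentence or two, and a section 7 entry. The second figure will look less favourable if data are missing and responders are observed. If nothing is missing, the two rates coincide. Trial conduct does not change.
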